#### **5.4.1.1 HCV Virologic Failure Criteria**

The following criteria will be considered evidence of HCV virologic failure for the purposes of subject management:

- Confirmed increase from nadir in HCV RNA (defined as 2 consecutive HCV RNA measurements of  $> 1 \log_{10}$  IU/mL above nadir) at any time point during treatment; or
- Confirmed HCV RNA  $\geq 100$  IU/mL (defined as 2 consecutive HCV RNA measurements  $\geq 100$  IU/mL) after HCV RNA  $<$  LLOQ during treatment.

When confirmatory testing is required it should be completed as soon as possible and the subject should remain on study treatment until the HCV virologic failure criterion has been confirmed. Subjects meeting a virologic failure criterion will be discontinued from

study drug and will continue to be followed in the Post-Treatment Period for the emergence and persistence of resistant viral variants until 144 weeks post-treatment.

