### **8.1.6 Resistance Analysis**

#### **8.1.6.1 HCV Drug-Resistance Analyses**

The secondary endpoint of resistance associated viral variants will be analyzed as follows. For all subjects in Part 1 and subjects with available samples in Part 2, full length NS3/4A or NS5A from baseline samples will be sequenced by NGS. For all subjects who experience virologic failure (on-treatment virologic failure or post-treatment relapse), full length NS3/4A and NS5A genes from the first sample after virologic failure with HCV RNA  $\geq 1000$  IU/mL will be sequenced by NGS. An appropriate subtype-specific prototypic reference sequence will be used for comparison with sequences from samples. Subjects treated with study drug who do not achieve SVR12 due to reasons other than virologic failure but have a time point with HCV RNA  $\geq 1000$  IU/mL after treatment discontinuation, will have the sample at that time point sequenced.

Only samples with an HCV RNA level of  $\geq 1000$  IU/mL will undergo sequence analysis in order to allow accurate assessment of products of amplification. Therefore, if the HCV RNA level at the time of HCV virologic failure or treatment discontinuation is  $< 1000$  IU/mL, the sample closest in time after HCV virologic failure/treatment discontinuation with an HCV RNA level  $\geq 1000$  IU/mL will be used. Included time

points for analyses on samples from subjects who do not achieve SVR12 are 1) the sample closest in time after failure/discontinuation with an HCV RNA level of  $\geq 1000$  IU/mL, and 2) 24 weeks post-DAA treatment, provided that resistance-associated substitutions were detected by NGS at the time of HCV virologic failure/treatment discontinuation.

For each DAA target, signature amino acid positions and a key subset of amino acid positions are listed in [Table 12](#). Appropriate subtype specific prototypic reference sequence will be used for comparison with sequences from samples.

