- Listings by subject and time point of all post-baseline substitutions at signature amino acid positions relative to the baseline amino acid sequence will be provided for each DAA target (NS3/4A and NS5A).

The persistence of post-baseline substitutions at signature amino acid positions for each target will be assessed by NGS through Post-Treatment Week 144. A listing by subject

and time point of all post-baseline substitutions relative to the baseline amino acid sequence will be provided for each DAA target.

If resistance-associated substitutions are not detected in a given target for a subject at the time of failure/discontinuation, then that target may not be sequenced in subsequent samples from that subject.

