**Post Treatment Period**

Activity	PT Wk 4	PT Wk 12	PT Wk 24	PT Wk 36	PT Wk 48	PT Wk 96	PT Wk 144	Premature D/C
Vital Signs, Weight, Height, Body Mass Index	X	X	X	X	X	X	X	X
Urine Pregnancy Test a	X							X a
Longitudinal Fibrotest and APRI		X			X	X	X	X
Hematology/Chemistry/Urinalysis b /Coagulation Panel b	X	X			X	X	X	X
HCC Assessment: Liver Ultrasound c			X			X	X	X
HCC Assessment: Alpha fetoprotein c			X		X	X	X	X
Concomitant Medication Assessment d	X	X	X	X	X	X	X	X
Adverse Event Assessment e	X	X	X	X	X	X	X	X
HCV RNA Samples	X	X	X	X	X	X	X	X
HCV Resistance Sample f	X	X	X	X	X	X	X	X
Patient Reported Outcome g		X						X g
HIV RNA Samples h	X	X						
Flow Cytometry h	X							

D/C = Discontinuation

- a. A positive urine pregnancy test requires a confirmatory serum test. (Refer to Section 5.3.1.1 [Pregnancy Test] for additional details.) Females who are experiencing menses or are nearing sexual maturation in the opinion of the PI or who are of childbearing potential should have urine pregnancy testing done through Post-Treatment Week 4. Pregnancy testing will be performed at PT Premature D/C visit only if the subject discontinues prior to PT Wk 4.
- b. Urinalysis will not be conducted after the Post-Treatment Week 4 visit. Urinalysis will be performed at PT Premature D/C visit only if the subject discontinues prior to PT Wk 4. The coagulation panel will be obtained at PTW4 for all patients. For non-cirrhotic subjects: Perform the coagulation panel at visits only if clinically indicated after post treatment Week 4.
- c. HCC assessment for subjects with compensated cirrhosis only.

- d. Concomitant medication will be collected for 30 days after study drug has been stopped, thereafter only antiviral medicines taken for the treatment of HCV and medications taken for SAEs will be recorded. See section 5.2.3.
- e. Non-serious AEs and all SAEs will be collected until 30 days post dosing. Only spontaneously reported SAEs will be collected thereafter. See Section 6.1.
- f. Resistance samples are only collected for patients that meet virologic failure criteria and should be drawn at the confirmatory visit, and if confirmed, at all subsequent visits.
- g. The PRO should be administered as the first study procedure. PRO will be accessed at the Premature D/C visit only if the subject discontinues prior to PT Wk 12.

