1b	36, 54, 55, 56, 80, 107, 122, 155, 156, 158, 168, 170, and 175	155, 156, 168
2, 3, 4, 5, 6, 1 – other (non 1a/1b)	36, 43, 54, 55, 56, 80, 155, 156, 166 (GT3 only) and 168	155, 156, 168
NS5A		
1a	24, 28, 29, 30, 31, 32, 58, 62, 92, and 93	24, 28, 30, 31, 58, 92, 93
1b	24, 28, 29, 30, 31, 32, 54, 58, 62, 92, and 93	24, 28, 30, 31, 58, 92, 93
2, 3, 4, 5, 6, 1 – other (non 1a/1b)	24, 28, 29, 30, 31, 32, 58, 92, and 93	24, 28, 30, 31, 58, 92, 93

Included time points for analyses on samples from subjects who do not achieve SVR₁₂ are 1) the sample closest in time after failure/discontinuation with an HCV RNA level of ≥ 1000 IU/mL, and 2) 24 weeks post-DAA treatment, provided that resistance-associated variants were detected at the time of failure/discontinuation.

The following definitions will be used in the resistance analyses:

- Baseline polymorphism: a polymorphism by NGS in a baseline sample ($\geq 2\%$ or $\geq 15\%$ prevalence within a subject's viral population depending on frequency threshold utilized) that was not present in the appropriate prototypic reference amino acid sequence for a given DAA target (NS3/4A or NS5A)
- Variant at signature amino acid position: variant (relative to reference) present by NGS at a detection threshold of 2% or 15% (depending on frequency threshold utilized) in a baseline or a post-baseline sample at a signature amino acid position
- Post-baseline variant: an amino acid variant in a post-baseline time point sample that was not detected at baseline ($< 2\%$) in the subject and is detectable in $\geq 2\%$ of the sequences from the post-baseline sample

- Enriched variant: variant present in both the baseline and a post-baseline sample whose prevalence in the post-baseline sample is at least 20 percentage points greater than the prevalence in the baseline sample [(post-baseline % – baseline %) ≥ 20]
- Treatment-emergent variant by NGS: A post-baseline variant or an enriched variant

Analysis will be performed separately for each cohort by HCV genotype/subtype within each listing.

Analysis 1: The following analyses will be performed for all subjects:

- A listing of all baseline polymorphisms (2% detection threshold) at signature amino acid positions for each DAA target (NS3 and NS5A) (ITT).

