Analysis 3: Analysis 3 will be applicable to Cohort 1 only. In subjects with or without baseline polymorphisms in NS3 only, in NS5A only, any in NS3, any in NS5A, any in NS3 or NS5A, and any in NS3 + NS5A at the *key subset of amino acid positions* at 15% detection threshold, the SVR₁₂ rate will be calculated, and the rates with or without polymorphisms will be compared using Fisher's exact test. Analysis will be separated by HCV subtype. The following tables will be provided (mITT-VF):

- Comparison of SVR₁₂ rates by subtype, and total (including all subtypes)
- Comparison of SVR₁₂ rates by genotype, and total (including all genotypes)

Analysis 4:

The following analyses will be performed for subjects who do not achieve SVR₁₂ (with separate summaries for subjects in PVF and non-PVF populations) and have post-baseline resistance data available:

- Listings by subject of all *treatment-emergent variants* relative to the baseline amino acid sequences will be provided for each DAA target (NS3/4A and NS5A).
- Listings by subject of all *variants at signature amino acid positions* in a post-baseline time point for each DAA target (NS3 and NS5A).
- The persistence of post-baseline variants at signature resistance-associated amino acid positions for each target (NS3 and NS5A) from subjects will be assessed at Post-Treatment Week 24. Listings by subject and time point of all treatment-emergent variants will be provided for each DAA target (NS3 and NS5A).

HCV Genotype/Subtype

Phylogenetic analysis will be conducted on HCV sequence from baseline samples for all subjects in Part 1, and from subjects with available sample in Part 2 in order to accurately determine subtype.

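### The documents disagree on how long resistance persistence is assessed: through PT Week 144 in parts of the protocol, only at PT Week 24 in the SAP and in another sentence of the protocol.

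*SAP*

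**What the plan says.** **Texts pointing to Week 144**

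- Protocol 8.1.6.1, after Table 12: persistence of post-baseline substitutions at signature positions "will be assessed by NGS through Post-Treatment Week 144".
- Protocol 5.4.1.1: a subject who meets a virologic failure criterion stops study drug and "will continue to be followed in the Post-Treatment Period for the emergence and persistence of resistant viral variants until 144 weeks post-treatment".
- Protocol Appendix C, Post Treatment Period: the resistance-sample row is marked at PT Weeks 4, 12, 24, 36, 48, 96 and 144. Note f restricts it to virologic failures and says samples "should be drawn at the confirmatory visit, and if confirmed, at all subsequent visits".
- SAP Table 4: analysis windows for HCV RNA and resistance endpoints run from PT Week 4 to PT Week 144.

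**Texts pointing to Week 24**

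- Protocol 8.1.6.1, before Table 12: for subjects without SVR12, the included time points are the first sample with HCV RNA of at least 1000 IU/mL after failure or discontinuation, and "24 weeks post-DAA treatment, provided that resistance-associated substitutions were detected by NGS at the time of HCV virologic failure/treatment discontinuation".
- SAP 10.8.1, after Table 14: the same two time points, the second being "24 weeks post-DAA treatment, provided that resistance-associated variants were detected at the time of failure/discontinuation".
- SAP 10.8.1, Analysis 4: persistence "will be assessed at Post-Treatment Week 24".

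The protocol also allows some later sequencing to be skipped. If a target shows no resistance-associated substitutions at failure or discontinuation, "then that target may not be sequenced in subsequent samples from that subject".

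**The concern.** Protocol 4.2 and SAP 4.1 both list emergence and persistence of viral variants as a secondary objective. For children with virologic failure, protocol 5.4.1.1 gives this as the reason for following them to 144 weeks. The SAP is the document that will be programmed, and it specifies no persistence analysis after Week 24.

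The sampling schedule and the analysis therefore do not match. Blood is drawn for resistance at four scheduled visits whose results have no assigned use under this objective. Each such sample is an estimated 6.0 mL on top of the scheduled draw (protocol Appendix D), taken from children as young as 3 years. A report that follows the SAP would also say nothing about variants that last beyond six months, although the protocol says this will be assessed.

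**Working it through.** The plan gives no figure to reproduce here. The check is a comparison of texts, then a count of visits, then an estimate of scale.

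**1. Visits without a specified persistence analysis.** The Appendix C resistance row marks PT Weeks 4, 12, 24, 36, 48, 96 and 144. Those after Week 24 are 36, 48, 96 and 144, so there are 4. SAP Table 4 has a window for each of them. With persistence assessed through Week 144, the scheduled time points from Week 24 onward rise from 1 to 5.

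**2. Follow-up not covered.** 144 − 24 = 120 weeks, and 120/144 = 83% of the post-treatment period.

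**3. Does any other SAP text bring the later samples in?** Analysis 4 promises listings by subject and time point without naming the time points. The sentence after Table 14 limits the included time points to two, so the listing cannot be relied on to show later samples. The Table 4 windows exist, but no persistence analysis refers to those after Week 24. Timing is not the obstacle, because SAP 4.4 places the final analysis after the 144-week visit.

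**4. How many children.** Inputs:

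- Planned enrolment is about 125 (protocol 8.2).
- Adult virologic failures among treatment-naïve and TE-PRS subjects number 23, one of them found to be a re-infection, leaving 22 (protocol 3.0).
- The matching denominator is 2256 (protocol Table 3).

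Assumption: the adult rate applies to children.

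- Rate: 22/2256 = 0.98%.
- Expected failures: 125 × 22/2256 = 1.2.
- Later samples: 1.2 × 4 = 4.9, about 5.
- Chance of no failure: (1 − 22/2256)^125 = 0.29.

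Range:

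- With 23/2256: 125 × 23/2256 = 1.3 children, 1.3 × 4 = about 5 samples, and a 28% chance of none.
- With twice the adult rate (44/2256), since protocol 3.2 allows that failure may be more frequent in children: 125 × 44/2256 = 2.4 children, 2.4 × 4 = about 10 samples, and (1 − 44/2256)^125 = 9% chance of none.

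Four samples per child is the number of scheduled visits. Fewer may be sequenced, because a sample needs HCV RNA of at least 1000 IU/mL and a target without substitutions at failure may be skipped. A premature-discontinuation visit could supply a sample at an unscheduled time.

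**The case against.** The strongest reply is that the SAP has not simply departed from the protocol. Its two-time-point rule repeats a sentence of protocol 8.1.6.1 almost exactly, and the secondary objective sets no duration, so a Week 24 assessment does address it. This stands. The protocol contradicts itself within 8.1.6.1, and the SAP follows one side of that contradiction. It does not remove the problem, because a programmer still cannot tell which sentence governs.

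Four stronger readings are tempting and are not supported:

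- **That the long follow-up exists to study persistence.** The synopsis gives its purpose as long-term safety and durability of SVR12, and protocol 5.1.3 adds growth and development. Resistance follow-up is one use, stated for virologic failures.
- **That SAP 12.1 concealed a departure.** SAP 3.0 elaborates Amendment 1 of 25 July 2017, whereas the supplied protocol's synopsis is dated 22 March 2019. Appendix E shows that the instruction in note f to sample at all later visits came in with the current amendment. Version lag may explain part of the mismatch, and the Amendment 1 text is not available to settle it.
- **That the SAP plainly discards the later data.** Table 4 and the by-time-point listing show that it is unclear with itself, though no later persistence analysis is specified.
- **That the number affected follows from all adults without SVR12 (50/2256), or that about a dozen samples is a ceiling.** That rate includes non-virologic reasons, and note f samples only virologic failures. An expected count multiplied by four is not an upper limit in any case.

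It is also fair to say that no primary result or confidence interval changes. The outputs concerned are by-subject listings for very few children.

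**Conclusion.** The concern holds as an inconsistency across both documents: one sentence of protocol 8.1.6.1, protocol 5.4.1.1, Appendix C note f and SAP Table 4 on one side; the other sentence of protocol 8.1.6.1 and two places in SAP 10.8.1 on the other. These are conflicting rules, not missing detail. If the SAP is followed as written, up to four scheduled samples per failing child fall outside the analysis of a stated secondary objective.

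The scale is small: about 1.2 children and 5 samples are expected, with roughly a 3 in 10 chance that no child is affected. Those figures rest on the adult virologic failure rate applying to about 125 children, on each failing child attending all four later visits, and on the samples being sequenceable. The visit count does not depend on the failure rate. The point deserves correction because a protocol commitment and repeated blood draws depend on it and the remedy is cheap, not because it threatens the trial's main conclusions.

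**What to change.** 1. **SAP 10.8.1, time-point sentence after Table 14, and Analysis 4 persistence bullet.** Change both together, since changing only one would leave the SAP contradicting itself. State that persistence is assessed by NGS at each available post-treatment sample with HCV RNA of at least 1000 IU/mL through PT Week 144, assigned to visits by the Table 4 windows. Keep the protocol's option not to re-sequence a target that had no substitutions at failure or discontinuation.
2. **SAP Analysis 4 listing.** State that the listing by subject and time point includes PT Weeks 36, 48, 96 and 144.
3. **Protocol 8.1.6.1.** Align the time-point sentence before Table 12 with the Week 144 sentence after it.

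If Week 24 is what the sponsor intends, the alternative is to record that reduction in SAP 12.1 and reconcile protocol 8.1.6.1, 5.4.1.1 and Appendix C note f with it.

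The cost of the main fix is a few lines of text and the sequencing of a handful of samples that Appendix C already has drawn. No extra visit, blood draw or analysis window is needed.

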10.9 Growth and Development

The following growth and development endpoints will be calculated in the ITT population.

- Growth rate at Post-Treatment Weeks 12, 48, 96 and 144 (defined as change in height over change in age from the previous visit)
- Weight z score⁵
- Height z score⁵
- Body mass index (BMI) z score⁵

Weight, height, and BMI z scores will be calculated using WHO published weight-for-age z score, height-for-age z score, and BMI-for-age z score tables, respectively. As described in Section 7.1, subjects who are older than 10 years at the time of the corresponding weight measurement will be excluded from the analyses of weight z score. If a subject becomes older than 19 years during the study, the WHO standards at 19 years old will be used to calculate height z score and BMI z score after 19 years old as these WHO standards are very close to the adult standards.

Growth rate will be summarized with N, mean and SD together, median and range together at each applicable post baseline visit by gender for all and for age group separately. Weight, height and BMI z scores will be summarized with N, mean and SD together, median and range together at each applicable post baseline visit for all and by age group.

10.10 Patient Reported Outcomes

The patient reported outcomes data will be analyzed in the ITT population.

At Baseline, End of Treatment, and Post-Treatment Premature Discontinuation, subjects will complete the PRO instrument, PedsQL, with the assistance of a parent/guardian (where allowed per local regulatory guidelines). The PedsQL Generic Core Scales is a 23 item questionnaire designed to measure the core dimension of health as defined by the

World Health Organization (WHO) along with role (school) functioning. The PedsQL consists of 4 Multidimensional Scales (Physical Functioning, Emotional Functioning, Social Functioning, and School Functioning) and 3 Summary Scores (Total Scale Score, Physical Health Summary Score, and Psychosocial Health Summary Score). Subjects who are older than 5-years of age and are able to read and understand the questions should complete the questionnaire by themselves. For subjects who are 5-years of age or younger or who are not comfortable with reading the questions, their parent(s)/guardian(s) should complete the parent/guardian proxy-report.

Across subjects enrolled in Part 1 and 2 (based on ITT population), summary statistics of change from baseline to Week 8 (only applicable to subjects assigned to 8 weeks of treatment), Week 12 (only applicable to subjects assigned to 12 weeks of treatment), Week 16 (only applicable to subjects assigned to 16 weeks of treatment) and Final Treatment Visit and Final PT Visit (n, mean, SD, minimum and maximum) of 3 summary scale scores will be provided by age group and overall. In addition the same summaries will be created separately for subjects who complete all the questionnaires by themselves and for subjects whose parent(s)/guardian(s) always complete the parent/guardian proxy-report.

If a subject starts another treatment for HCV, then all PRO values for this subject measured on or after the start date of the new HCV treatment will be excluded from analyses.

11.0 Safety Analysis

11.1 General Considerations

Safety analyses will be performed using the safety population overall and by age group.

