## **4.0 Study Objective**

### **4.1 Primary Objective**

The primary objectives are to:

- assess the steady state AUC, and to assess the pharmacokinetics (PK) of GLE/PIB in pediatric subjects following multiple dosing by age group;
- evaluate the safety and tolerability of GLE/PIB by age group, cirrhosis status and across all subjects

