### **8.1.5 Safety**

The secondary safety endpoints are rates of adverse events and clinically significant laboratory abnormalities. All subjects who receive at least one dose of study drug will be included in the safety analyses. The safety analysis will be carried out for all subjects by for each age group and overall. Subjects who receive a dose lower than the final dose chosen for the subject's age group might be summarized separately. A listing of any SAEs recorded in the Post-Treatment Period will be included.

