5.1.3 Safety Population

All subjects who receive at least one dose of study drug will be included in the safety population. Safety analysis will be performed on the safety population overall and by age group.

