7.1 Demographic and Baseline Characteristics

Categorical demographic and baseline characteristic variables will be summarized with the number and percentage of subjects. Continuous variables will be summarized with descriptive statistics (number of non-missing observations, mean, standard deviation, median, maximum and minimum).

Continuous demographic variables include age, weight, height, and body mass index (BMI), BMI z score (BMI z score will be calculated using WHO published BMI-for-age z score tables),⁵ weight and height z scores (weight and height z scores will be calculated using WHO published weight-for-age z score and height-for-age z score tables).

Categorical demographic variables include sex, race, black race (black or non-black), ethnicity, age category (≥ 3 to < 6 years, ≥ 6 to < 9 years, ≥ 9 to < 12 years, ≥ 12 to < 18 years), birth year, weight category (≥ 12 to < 20 kg, ≥ 20 to < 30 kg, ≥ 30 to < 45 kg, ≥ 45 kg), weight z score category (< -1 , -1 to 1 , > 1), Height z-score category (< -1 , -1 to 1 , > 1), BMI z-score category (< -1 , -1 to 1 , > 1) country, and geographic region (North America, Europe, or Japan).

Weight-for-age reference data are not available beyond age 10 because this indicator does not distinguish between height and body mass in an age period where many children are experiencing the pubertal growth spurt and may appear as having excess weight (by weight-for-age) when in fact they are just tall. Subjects who are older than 10 years at the time of the corresponding weight measurement will be excluded from the summary of weight z score.

When defining geographic region, sites in the United States, Puerto Rico, and Canada will be grouped under North America; sites in Belgium, Germany, Russia, Spain and the United Kingdom will be grouped under Europe; sites in Japan will be grouped together as Japan.

Continuous baseline characteristics include baseline \log_{10} HCV RNA level, creatinine clearance, eGFR, platelet count, albumin, GGT, alpha fetoprotein (for cirrhotic subjects only), Fibrotest, APRI, FIB-4, AST, ALT, total, direct, and indirect bilirubin for all subjects.

Categorical baseline characteristics include:

- HCV genotype and subtype (using central laboratory results and final genotype/subtype results, see Section 10.8);
- Prior HCV treatment history (naïve or experienced);
- For treatment-experienced subjects, type of previous regimen (IFN- or SOF-based);

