Baseline Fibrosis Stage, Metavir Equivalents	Liver Biopsy Metavir, Batts Ludwig, Knodell, IASL, Scheuer, New Inuyama or Laennec Score	Liver Biopsy Ishak Score	FibroScan (kPa)	FibroTest*
F0 – F1	0 or 1	0, 1, or 2	< 8.8	≤ 0.48
F2	2	3	≥ 8.8 to < 9.6	0.49 to 0.58
F3	3	4	≥ 9.6 to < 12.5	0.59 to 0.72
F4	4	≥ 5	≥ 12, 5	≥ 0.73

* APRI will not be used to derive Baseline Fibrosis Stage. However, per inclusion/exclusion criteria, subjects need to have concordant FibroTest and APRI scores in order to determine eligibility.

Presence or absence of cirrhosis will be determined as collected in EDC ("What is the subject's cirrhosis status?" – "cirrhotic" or "non-cirrhotic").

Baseline Child-Pugh score is the sum of the points assigned for each of the five observed findings as defined in [Table 12](#).

Table 12. Child-Pugh Classification of Severity of Cirrhosis

Parameter	Points Assigned for Observed Findings		
	1	2	3
Total bilirubin, µmol/L (mg/dL)	< 34.2 (< 2)	34.2 – 51.3 (2 – 3)	> 51.3 (> 3)
Serum albumin, g/L (g/dL)	> 35 (> 3.5)	28 – 35 (2.8 – 3.5)	< 28 (< 2.8)
INR	< 1.7	1.7 – 2.3	> 2.3
Ascites*	None	Slight	Moderate to severe
Hepatic encephalopathy**	None	Grade 1 or 2 (or suppressed with medication)	Grade 3 or 4 (or refractory)

* None.

Slight ascites = Ascites detectable only by ultrasound examination.

Moderate ascites = Ascites manifested by moderate symmetrical distension of the abdomen.

Severe ascites = Large or gross ascites with marked abdominal distension.

** None: normal consciousness, personality, neurological examination, electroencephalogram.

Grade 1: restless, sleep disturbed, irritable/agitated, tremor, impaired handwriting, 5 cps waves.

Grade 2: lethargic, time-disoriented, inappropriate behavior, asterixis, ataxia, slow triphasic waves.

Grade 3: somnolent, stuporous, place-disoriented, hyperactive reflexes, rigidity, slower waves.

Grade 4: unarousable coma, no personality/behavior, decerebrate, slow 2 to 3 cps delta activity.

Baseline APRI and FIB-4 are defined as the equations below. Subjects who do not have concurrent AST and platelet values at baseline will be excluded from the summary of baseline APRI. Age is defined in years at baseline. Subjects who do not have concurrent values of AST, ALT, and platelet count at baseline, or subjects who are missing age will be excluded from the summary of FIB-4.

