10.6 Efficacy Subgroup Analysis

The percentage of subjects with SVR₁₂ in the ITT population will be calculated along with the corresponding 2-sided 95% Wilson score confidence interval for the following subgroups if applicable:

- HCV genotype (1, 2, 3, 4, 5, or 6);
- Prior HCV treatment history (treatment-naïve or treatment-experienced);
- For treatment-experienced subjects, type of previous regimen (IFN- or SOF-based);
- Sex (male or female);
- Race (black or non-black);

- Ethnicity (Hispanic or Latino, Not Hispanic or Latino);
- Geographic region (North America, Europe, Japan);
- Height z-score (< -1 , -1 to 1 or > 1);
- BMI z-score (< -1 , -1 to 1 or > 1);
- Drug compliance ($< 80\%$ versus $\geq 80\%$)
- Baseline fibrosis stage (F0 – F1, F2, F3 or F4);
- Cirrhosis status (yes/no);
- Baseline HCV RNA level ($< 1,000,000$, $\geq 1,000,000$ to $< 2,000,000$, $\geq 2,000,000$ IU/mL);
- Baseline platelet count (< 90 or $\geq 90 \times 10^9/L$);
- Baseline albumin (< 35 or ≥ 35 g/L);
- Injection drug user (yes, within last 12 months; yes, more than 12 months ago; or no);
- Concomitant use of Proton Pump Inhibitors (PPIs) (yes/no).
- Concomitant use of Statins (yes/no);

For subjects with cirrhosis only:

- Baseline Child-Pugh Score (5, 6, or > 6).
- Baseline platelets (< 90 or $\geq 90 \times 10^9/L$);
- Baseline albumin (< 35 or ≥ 35 g/L);

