Creatinine	> ULN – 1.5 × ULN	> 1.5 – 3 × ULN	> 3 – 6 × ULN	> 6 × ULN
Creatinine clearance	< LLN – 60 mL/min	< 60 – 30 mL/min	< 30 – 15 mL/min	< 15 mL/min
Albumin	< LLN – 30 g/L	< 30 – 20 g/L	< 20 g/L	--

Assessment of Hepatic Laboratory Values

The number and percentage of subjects in each age group and overall meeting the following criteria during treatment will be summarized:

- Post nadir (preceding value is lower than the subsequent value)
ALT > 5 × ULN (regardless of grade change);
- Total bilirubin ≥ 2 × ULN and > baseline (i.e., a post-baseline value must be more extreme than the baseline value to be considered)
- Post nadir ALT > 3 × ULN and total bilirubin > 2 × ULN (Hy's law quadrant)

- Post nadir ALT > 3 × ULN and total bilirubin ≤ 2 × ULN (Temple's corollary quadrant)

Four listings (one for each bullet above) of all liver function tests including ALT, AST, total, indirect and direct bilirubin, ratio of direct to total bilirubin, and alkaline phosphatase values will be provided for each subject who met the criterion defined above.

Hepatic Laboratory Abnormalities of Interest

Among the labs assessed under "Assessment of Hepatic Laboratory Values" the following criteria are of interest:

- Confirmed post-nadir ALT > 5 × ULN;
- Post nadir ALT > 3 × ULN and a concurrent total bilirubin > 2 × ULN with direct bilirubin/total bilirubin ratio > 0.4

Two listings (one for each bullet) of all liver function tests including ALT, AST, total, indirect and direct bilirubin, ratio of direct to total bilirubin, and alkaline phosphatase values will be provided for each subject who met the criterion defined above.

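### Safety by cirrhosis status is part of the primary objective, but no planned safety table or listing in the protocol or SAP identifies cirrhosis status

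*SAP*

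**What the plan says.** Protocol 4.1 sets as a primary objective to "evaluate the safety and tolerability of GLE/PIB by age group, cirrhosis status and across all subjects". SAP 4.1 repeats it.

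The analysis sections name two of these three dimensions. SAP 5.1.3: "Safety analysis will be performed on the safety population overall and by age group". SAP 11.1: "Safety analyses will be performed using the safety population overall and by age group". For the hepatic laboratory criteria, SAP 11.3.2: "The number and percentage of subjects in each age group and overall meeting the following criteria during treatment will be summarized". Protocol 8.1.5: "The safety analysis will be carried out for all subjects by for each age group and overall". Protocol 8.1.5 also allows subjects on a dose below the final one to be summarised separately, and protocol 8.1.5.1 leaves room for unspecified further adverse event analyses.

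The variable itself is defined. SAP 7.1 states "Presence or absence of cirrhosis will be determined as collected in EDC". Cirrhosis status is tabulated as a baseline characteristic, and SAP 10.6 uses it as an SVR12 subgroup.

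On two smaller points, protocol 6.1.3 says that the sponsor treats an event as associated when the investigator gives no causality or cannot assess it. SAP 11.2.2 counts the most severe occurrence of a preferred term in the severity tables. A later paragraph of the same section puts the subject under *unknown* if any occurrence of that term has no grade, except where another is Grade 5.

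**The concern.** The SAP splits efficacy by cirrhosis status, but not safety, although the primary safety objective is the one that names it. If the plan is followed as written, the study report will have no output that answers that part of the objective, and a reader could not tell whether safety in cirrhotic children was examined and unremarkable or not examined. Protocol 3.0 makes the comparison in the adult programme (1,977 subjects without cirrhosis, 288 with). No paediatric counterpart is planned.

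**Working it through.** The main point is a comparison of texts. There is no planned figure to reproduce.

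**Objective against output**

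| Planned safety output | Where | Grouping stated |
|---|---|---|
| Safety analyses in general | Protocol 8.1 and 8.1.5; SAP 5.1.3 and 11.1 | Age group, overall |
| Adverse event overview; SOC and PT tables | SAP 11.2.2 | Age group, overall |
| Adverse events of special interest | SAP 11.2.3 | None stated |
| Laboratory changes and toxicity grades | SAP 11.3.2 | Age group, overall |
| Hepatic laboratory criteria | SAP 11.3.2 | Age group, overall |
| Vital signs | SAP 11.4.2 | Age group, overall |

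Cirrhosis status appears in none of these. The nearest thing is alpha fetoprotein, which is scheduled only in cirrhotic subjects (protocol Appendix C). A summary of it is limited to them by collection and gives no wider view of their safety. The five items in SAP 12.1 do not include the omission.

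**How many subjects are concerned**

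Inputs: 125 subjects (protocol 8.2). The share with cirrhosis, p, is not given. Protocol 3.0 cites about 2% of children progressing to advanced liver disease, used here as an assumed proxy with a range of 1% to 5%. Expected number = 125 × p; chance of none = (1 − p)^125; chance of fewer than 5 from the binomial distribution.

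| p | Expected number | Chance of none | Chance of fewer than 5 |
|---|---|---|---|
| 1% | 1.25 | 28.5% | 99.1% |
| 2% | 2.5 | 8.0% | 89.3% |
| 5% | 6.25 | 0.2% | 24.6% |

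With no events among n subjects, the one-sided 95% upper limit is 1 − 0.05^(1/n): 63% for n = 3 and 39% for n = 6. Any split can therefore only be descriptive.

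**Smaller points**

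- *Causality.* Only subjects with an adverse event but no related one can move. At the adult rates (protocol Table 4) that is (1,529 − 929)/2,265 = 26.5%, or 33.1 of 125. If 1% to 5% of these lacked a causality assessment (assumed), 0.3 to 1.7 subjects would move, which is 0.3 to 1.3 percentage points.
- *Severity.* At the adult rate, 65/2,265 × 125 = 3.6 subjects have an event of Grade 3 or higher. If 1% to 5% of these had an ungraded repeat of the same term (assumed), 0.04 to 0.18 subjects would be shown as *unknown*.

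**The case against.** **Most of the data will be listed anyway.** SAP 11.2.2 plans a listing of treatment-emergent adverse events with subject numbers. SAP 11.2.4 adds serious events and discontinuations, and SAP 11.3.2 lists laboratory values for every subject who rises to Grade 2 or higher. With two or three cirrhotic subjects, a reader with access to cirrhosis status could assemble the picture. This stands and sets the size of the point. A reader might infer that cirrhotic safety data would be lost, and the documents do not support that. What is missing is any output that labels or sorts by cirrhosis status.

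**Further analyses are allowed.** Protocol 8.1.5.1 permits them, but it neither names cirrhosis nor commits to anything. That is thin support for a named element of a primary objective.

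**The objective could be narrowed instead.** That would remove the contradiction, but it would give up something the plan set out to assess when the data are already collected.

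**Stronger readings that do not hold.**

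- A reader might infer that the pooled INR toxicity row is distorted, because coagulation is scheduled at all treatment visits in cirrhotic subjects and less often in others (Appendix C, Treatment Period, note h). That row counts subjects by their maximum grade, so at the assumed 2% cirrhotic subjects can move it by at most 2.5/125 = 2 percentage points. The SAP counts post-baseline values, and a coagulation panel is taken in all subjects at Post-Treatment Week 4.
- A reader might infer that follow-up Child-Pugh scores go unreported. Protocol 5.3.1.1 and Appendix C schedule the score only at screening.
- A reader might infer that the SAP dropped an analysis the protocol had planned. Protocol 8.1.5 does not plan it either, and the SAP was written against an earlier amendment that is not among the documents. The mismatch does not depend on this, because SAP 4.1 states the objective itself.

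**The smaller points are slight.** The *unknown* row in the maximum-relationship table is labelled as the investigator's assessment and does not conflict with protocol 6.1.3. What remains is that *DAA-related* is used in several tables without saying how missing causality counts. For severity, separate tables of Grade 3 or higher events keep those events visible.

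**Conclusion.** The mismatch is certain from the text: both documents promise safety by cirrhosis status, and neither plans an output that shows it. Its impact is low. It concerns the reporting of a stated objective, in roughly 1 to 6 subjects under the assumed 1% to 5%, and cannot support a comparison. The 2% is a figure for advanced liver disease in children generally, not for cirrhosis in enrolled subjects, so the expected number is a guide to format only. The causality and severity points are real ambiguities with very small expected effects. Their frequencies are assumed and are probably low, since protocol 6.1 has the investigator record severity and relationship for each event.

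**What to change.** In SAP 5.1.3 and 11.1 and in protocol 8.1.5, add baseline cirrhosis status, as collected in EDC, as a grouping for the adverse event overview (SAP 11.2.2) and for the laboratory toxicity and hepatic laboratory summaries (SAP 11.3.2). If only a few subjects are cirrhotic, replace these tables with a by-subject listing of their treatment-emergent adverse events and graded laboratory values. Fewer than 5 is a workable cut-off, offered as a convention. If no cirrhotic subject is enrolled, say so. Label the output descriptive.

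In SAP 11.2.2, state whether tables headed *DAA-related* count missing or unassessable causality as associated, in line with protocol 6.1.3, and footnote the number. In the maximum-severity tables, use the highest known grade and keep *unknown* for subjects with no graded occurrence of the term.

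The cost is wording in those sections and minor programming on data already collected. No new assessments are needed. Counting missing causality as associated may raise the related-event rates slightly.
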